11.1. Specsavers follow up

If a participant fails to attend 3 consecutive OCT appointments they will be removed from further follow up at Specsavers. If the participant can then be contacted by the IIH-Advance trials team, is keen to re-engage and is happy to remain in the research study an OCT appointment will be re-booked.

12. Adverse Event Reporting

12.1. Definitions

Table 3: Adverse event reporting definitions

Severity Definitions	Mild Moderate Severe	Awareness of signs or symptoms that do not interfere with the participant's usual activity or are transient and resolved without treatment and with no sequelae. A sign or symptom, which interferes with the participant's usual activity. Incapacity with inability to do work or perform usual activities.
Adverse Event	AE	Any untoward medical occurrence in a participant participating in the trial which does not necessarily have a causal relationship with the intervention received.
Related Event	N/A	An event which resulted from the administration of any of the research procedures.
Serious Adverse Event	SAE	An untoward occurrence that: Results in death

		Is life-threatening* Requires hospitalisation or prolongation of existing hospitalisation Results in persistent or significant disability or incapacity Consists of a congenital anomaly/ birth defect Or is otherwise considered medically significant by the Investigator**
Unexpected Event	N/A	The type of event that is not listed in the protocol as an expected occurrence.
Related and Unexpected Serious Adverse Event	N/A	A SAE that meets both the definition of a Related and Unexpected Event.

* The term life-threatening is defined as diseases or conditions where the likelihood of death is high unless the course of the disease is interrupted.

** Medical events that may not be immediately life-threatening or result in death or hospitalisation but may jeopardise the participant or may require intervention to prevent one of the other outcomes listed in the definitions above.

12.2. Adverse event recording – general

The recording and reporting of adverse events will be in accordance with the UK Policy Framework for Health and Social Care Research and the requirements of the Health Research Authority (HRA). Definitions for adverse event reporting are listed in **Table 3: Adverse Event reporting definitions in section 12.1**.

It is routine practice in NHS research to record adverse events in the participant's medical notes and it is also recommended that this includes the documentation of the assessment of severity and seriousness and of causality (relatedness) in relation to the intervention in accordance with the protocol. We will therefore mirror what would be expected in an NHS participant's notes; a notes field will be created on the eCRF for each follow up assessment to serve the function of medical notes. The trial researcher will review all potential AEs with participants at each appointment and record the discussions, including an evaluation of these events.

12.3. Adverse event reporting in IIH-Advance

The reporting period for adverse events in IIH-Advance will be from the day of randomisation until the end of follow up (i.e. 5 weeks after the last dose, if having taken Tirzepatide). The safety profile for this trial population and rapid weight loss regimens are well characterised so a strategy of targeted reporting of adverse events will not affect the safety of participants: only Serious Adverse Events (SAEs) will be reported.

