3.1.4. Trial exit at all stages

In all stages, participants who receive Tirzepatide will have a final well-being follow up appointment with the trial researcher 5 weeks after the last dose of the drug, which completes their involvement in the trial.

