7.2.3. Pregnancy

Tirzepatide is contraindicated in pregnancy due to the lack of data in humans to determine the risk of birth effects, miscarriage, or other adverse outcomes. Tirzepatide is not recommended in women wanting to become pregnant and should be discontinued for one month before a planned pregnancy. If a participant becomes pregnant whilst allocated to Tirzepatide, they will be instructed to immediately stop taking it.

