9.6. Follow up (final dose of Tirzepatide + 5 weeks)

Five weeks after their final dose of Tirzepatide (whenever this occurs for each participant), all participants will be invited to attend a short follow up call, where a health and wellbeing check will be carried out as per recommended routine practice when losing weight using Tirzepatide. They will then leave the trial.

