Informed consent is defined as the process of learning key facts about a clinical trial before deciding whether or not to participate. It is a continuous and dynamic process and participants should be asked about their ongoing willingness to continue participation at all visits. Participants should be aware from the beginning that they can freely withdraw (cease to participate) from the trial at any time. A participant may wish to cease to participate in a particular aspect of the trial. The changes in levels of participation within the trial are categorised in the following ways:

No trial intervention: The participant would no longer like to receive the trial intervention, but is willing to be followed up in accordance with the schedule of assessments and if applicable using any central UK NHS bodies for long-term outcomes (i.e. the participant has agreed that data can be collected and used in the trial analysis).

No further data collection: The participant is not willing to be followed up in any way for the purposes of the trial AND does not wish for any further data to be collected (i.e. only data collected prior to any changes of levels in participation can be used in the trial analysis).

The details of changes of levels in participation within trial (date, reason and category of status change) will be entered onto the Participant Change of Status Form on the EDC. Participants can change their level of participation without giving a reason.

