12.5.3. Provision of SAE follow up information

Following reporting of an SAE for a participant, the participant should be followed up until resolution or stabilisation of the event. Follow up information should be provided using the SAE reference number provided by the Trial Office.

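### Adverse event reporting closes 5 weeks after the last dose, so a birth defect, which the protocol defines as an SAE, would usually go unrecorded

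*Protocol*

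**What the plan says.** - **Definition.** Section 12.1, Table 3, includes this criterion for a serious adverse event: "Consists of a congenital anomaly/ birth defect". The event is on neither the exempt list (12.4.1) nor the non-expedited list (12.4.2), so 12.4.3 calls for a report within 24 hours.
- **Window.** Section 12.3 sets the reporting period as "from the day of randomisation until the end of follow up (i.e. 5 weeks after the last dose, if having taken Tirzepatide". It limits reporting to SAEs and justifies this by a well characterised safety profile.
- **Pregnancy.** Section 7.2.3 gives the reason for the contraindication as "due to the lack of data in humans to determine the risk of birth effects, miscarriage, or other adverse outcomes". The only action it sets is: "If a participant becomes pregnant whilst allocated to Tirzepatide, they will be instructed to immediately stop taking it".
- **Exit.** Section 3.1.4 places the final contact "5 weeks after the last dose of the drug, which completes their involvement in the trial". Section 9.6 says of participants after that call: "They will then leave the trial".
- **Follow-up beyond the window.** Section 12.5.3 says: "Following reporting of an SAE for a participant, the participant should be followed up until resolution or stabilisation of the event".
- **Staying in off drug.** Section 11 lets a participant give up the intervention and remain in the trial if she "is willing to be followed up in accordance with the schedule of assessments".

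The rest of the pregnancy text covers exclusion, contraception (4.2, 4.3, 7.2.4) and urine tests, which Table 1 schedules at baseline, month 6 and month 12. The NHS data linkage in 5.7.1 is optional, meant for possible later research and dependent on new funding.

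**The concern.** The protocol classes an event as serious and then usually ends reporting before that event can be seen. Stopping the drug on discovery of a pregnancy fixes the date of the last dose and so brings closure forward. Section 12.5.3 does not help, because it needs an SAE already reported and Table 3 does not list pregnancy itself as one.

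The justification in 12.3 does not extend to pregnancy, where 7.2.3 says human data are lacking. The Trial Summary describes IIH as occurring mainly in women of childbearing age. At stake is whether the trial, and its DMC, would learn the outcome of the few exposed pregnancies that may occur. Efficacy conclusions are not at stake.

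**Working it through.** The protocol gives no figure for this, so the check is a timeline.

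**Inputs from the protocol**
- A month is 28 days (Definitions), so a 6-month stage is 6 × 28 = 168 days = 24 weeks. Month 12 is week 48 and month 18 is week 72.
- Reporting closes 5 weeks after the last dose (12.3).
- 86 participants, randomised 1:1 at R1 and again at R2 (6.2, 6.3); 25% attrition (16.1).

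**Assumptions, not in the protocol**
- Conception to birth, g: 35 to 40 weeks.
- Conception to stopping the drug, s: 2 to 14 weeks.
- Pregnancy rate: 1 to 5 per 100 person-years.

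**1. She stops the drug and leaves at the 5-week call.** Weeks from closure to birth = g − (s + 5).
- Shortest: 35 − (14 + 5) = 16.
- Longest: 40 − (2 + 5) = 33.
- With narrower ranges (g 35 to 38, s 2 to 12): 35 − 17 = 18 to 38 − 7 = 31.

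**2. Conception t = 0 to 5 weeks after the last dose.** Weeks from closure to birth = g − (5 − t).
- 35 − 5 = 30 to 40 − 0 = 40.

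**3. Exposed in R1, remains in scheduled visits off drug.**
- Visits to month 12: birth falls inside only if conception came before week 48 − 40 = 8 to week 48 − 35 = 13.
- Visits to month 18 (R2 standard of care, then SA3): the latest R1 conception gives birth by week 24 + 40 = 64. If conceived 5 weeks after R1 ends, birth is by week 29 + 40 = 69. Both precede week 72.
- This path is uncertain. Table 1 has an eligibility check and a pregnancy test at months 6 and 12. The protocol does not say whether a pregnant participant would continue, or whether the 12.3 window would stay open for her.

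**4. Conception during R2 Tirzepatide or SA3.** The most favourable case is conception on day 1 of the stage.
- After the end-of-stage visit: 35 − 24 = 11 to 40 − 24 = 16 weeks.
- After a 5-week call following a full course: 35 − 29 = 6 to 40 − 29 = 11 weeks.

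So no such conception reaches birth within scheduled contact.

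**5. How many pregnancies?** As an upper bound, let all 86 be re-randomised, giving four paths of 86 / 4 = 21.5 participants:

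| Path (R1, R2, SA3) | Weeks on drug | Post-dose weeks |
|---|---|---|
| Tirzepatide, Tirzepatide | 48 | 5 |
| Tirzepatide, standard of care, Tirzepatide | 48 | 10 |
| Standard of care, Tirzepatide | 24 | 5 |
| Standard of care, standard of care, Tirzepatide | 24 | 5 |
| Sum | 144 | 25 |

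- On drug: 144 × 21.5 = 3096 weeks.
- Post-dose: 25 × 21.5 = 537.5 weeks.
- Total: 3633.5 / 52 = 69.9 person-years; at 75% retention, 69.9 × 0.75 = 52.4.
- Pregnancies: 69.9 × 0.01 to 69.9 × 0.05 = 0.7 to 3.5; at 75% retention, 0.5 to 2.6.

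**The case against.** The strongest reply is that Table 3 also has a discretionary criterion: an event the investigator judges medically significant. Its footnote covers events that may need intervention to prevent another listed outcome, and a birth defect is one of those. A pregnancy exposed to a contraindicated drug could be reported that way, and 12.5.3 would then carry follow-up past 5 weeks. The route exists, but it rests on individual judgement and the protocol nowhere applies it to pregnancy. It cannot be relied on.

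Other points deserve weight:

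- **Contraception.** Highly effective contraception is required through treatment and for 5 weeks afterwards, with a negative test before randomisation. This lowers the number of pregnancies but does not close the gap. Section 4.3 accepts oral hormonal methods, while 7.2.4 says that reduced efficacy of these at high BMI cannot be ruled out and only advises a switch or an added barrier.
- **Reading of the window.** The period in 12.3 could be taken to last through all scheduled follow-up, with the 5 weeks describing the ordinary exit. That would help some R1 conceptions, as step 3 shows, but none in step 4.
- **No contradiction in terms.** A seriousness list and a bounded window can coexist. That is fair: the fault is an omission in the window rule.
- **Frequency.** The person-years are an upper bound. Standard-of-care responders and Tirzepatide non-responders are not re-randomised, and the count includes men and women who cannot conceive. The true figure may be below one.
- **Context.** The drug is licensed and the trial is not a CTIMP. Table 7 is not an exhaustive list of forms, and the consent pages are not available here, so a pregnancy form or consent line may exist. The stated 12.3 window would still need an exception.

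**Conclusion.** The concern holds. As written, the reporting rule would usually miss the outcome of a pregnancy exposed to Tirzepatide. For a participant who stops and exits, closure precedes birth by 16 to 33 weeks. The exceptions are an early event inside the window, such as a miscarriage that meets an SAE criterion, and some R1 conceptions if the participant stays in visits and reporting is taken to stay open.

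The intervals rest on the assumed times to birth and to stopping the drug; a birth earlier than 35 weeks from conception would shorten them. The expected count of 0.5 to 3.5 rests on an assumed pregnancy rate and on exposure that is overstated. This is a safety-reporting rule that belongs in the protocol, not an analysis detail that could be left to the SAP. It should be corrected, though it has no bearing on the primary comparison.

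**What to change.** Add an exception to section 12.3, cross-referenced from 7.2.3 and 9.6:

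- Any pregnancy conceived from the first dose to 5 weeks after the last dose is notified to the Trial Office.
- With consent, it is followed to its outcome, whether or not the participant has otherwise left the trial.
- Any congenital anomaly is reported as an SAE regardless of the 5-week limit.

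The cost is one form, one consent line and a few calls for the few pregnancies expected. The sample size and primary analysis do not change.

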12.4. Serious Adverse Events reporting in IIH-Advance

For all SAEs, the Trial Researcher must do one of the following:

1. **Record safety reporting-exempt SAEs** in the EDC notes field notes but **not report** them to the Trial Office on an SAE form as per **Section 12.4.1** Serious Adverse Events not requiring reporting to the Trial Office.
2. **Report SAEs to the Trial Office in a non-expedited manner.** This can only be done for the pre-defined subset of SAEs as per **Section 12.4.2** Serious Adverse Events requiring non-expedited reporting to the Trial Office.

3. **Report SAEs to the Trial Office in an expedited manner** (within 24 hours of the site research team becoming aware of the event). All SAEs not covered by the above 2 categories must be reported as per **Section 12.5** SAE Reporting process.

12.4.1. Serious Adverse Events not requiring reporting to the Trial Office

The following will not be considered critical to evaluations of the safety of the trial:

- Pre-planned hospitalisation
- General hospital attendance lasting less than 24 hours
- Hospitalisation for routine treatment or monitoring of IIH, not associated with any deterioration in condition or trial procedures
- Treatment, which was elective or pre-planned, for a pre-existing condition that is unrelated to the indication under study
- Admission to a hospital or other institution for general care (not related to IIH or trial intervention), not associated with any deterioration in condition or trial procedures

All events which meet the definition of serious must be recorded in the participant notes field on the EDC as per adverse events in **section 12.2**, including the causality and severity, throughout the participant's time in the trial, but for trial purposes these events do not require reporting on the SAE Form. Such events are "safety reporting exempt".

12.4.2. Serious Adverse Events requiring non-expedited reporting to the Trial Office

Where the safety profile is well established, the causal relationship between the intervention (or the participant's underlying condition) and the SAE may be known. That is, such events are protocol-defined as "expected" (see **Section 12.5.2**). Such events should still be recorded by the trial team in the participant's notes field on the EDC, and reported to the Trial Office on the trial specific SAE form **within 4 weeks of becoming aware of the event**. These events do not require expedited reporting (i.e. immediately on becoming aware of the event) since the assessment of expectedness for the specified events has been pre-defined. These are:

- Hospitalisation due to exacerbation of IIH
- Hospitalisation for treatment of IIH

12.4.3. Serious Adverse Events requiring expedited reporting to the Trial Office

All SAEs not listed in **Sections 12.4.1** and **12.4.2** must be reported to the Trial Office on a trial specific SAE form within 24 hours of the site research team becoming aware of the event.

12.5. SAE Reporting process

To report an SAE to the Trial Office, the trial researcher must complete the trial specific SAE form on the EDC. The completed form should be submitted to the Trial Office in accordance with the timelines given in **Sections 12.4.2** and **12.4.3**.

To report an SAE, complete the SAE eCRF on the Electronic Data Capture System.

Where an SAE form has been completed initially by someone other than a medically qualified researcher, the electronic SAE form must be reviewed and approved by a medically qualified researcher to confirm the causality and severity assessments. When an SAE form has been entered onto the EDC, it will be allocated a unique reference number.

12.5.1. Assessment of causality of an SAE

When completing the SAE form, a Trial Doctor (i.e. a medically qualified researcher) will be asked to define the nature of the seriousness and causality of the event.

In defining the causality, the Trial Doctor must consider if any concomitant events or medications may have contributed to the event and, where this is so, these events or medications should be reported on the SAE form. It is not necessary to report concomitant events or medications which did not contribute to the event.

As per **Table 4: Categories of causality**, all events considered to be 'possibly', 'probably', or 'definitely' related to the intervention will be reported by the trial office as 'related'; all events considered by the assessing medically qualified researcher to be 'unlikely' or 'unrelated' to the intervention will be reported by the trials office as 'unrelated'. The same categorisation should be used when describing AEs and safety reporting-exempt SAEs in the source data.

Table 4: Categories of causality

Category	Definition	Causality
Definitely	There is clear evidence to suggest a causal relationship, and other possible contributing factors can be ruled out.	Related
Probably	There is evidence to suggest a causal relationship, and the influence of other factors is unlikely.	
Possibly	There is some evidence to suggest a causal relationship. However, the influence of other factors may have contributed to the event (e.g., the participant's clinical condition, other concomitant events or medication)	
Unlikely	There is little evidence to suggest there is a causal relationship. There is another reasonable explanation for the event (e.g., the participant's clinical condition, other concomitant events or medication).	Unrelated
Not related	There is no evidence of any causal relationship.	

On receipt of an SAE Form, the Trial Office will alert the CI or delegate(s) who will independently* review the causality of the SAE. An SAE judged by the assessing Trial Doctor or CI (or delegate) to have a reasonable causal relationship ("Related" as per Table 4: Categories of causality) with the intervention will be regarded as a related SAE. The severity and causality assessment given by the Trial Doctor will not be downgraded by the CI or delegate. If the CI or delegate disagrees with the assessing Trial Doctor's causality assessment, the opinion of both parties will be documented, and where the event requires further reporting, the opinion will be provided with the report.

*Where the CI is also the assessing Trial Doctor, an independent clinical causality review will be performed.

12.5.2. Assessment of expectedness of an SAE by the CI

The CI or delegate will also assess all related SAEs for expectedness with reference to the criteria in **Table 5: Categories of expectedness**.

Table 5: Categories of expectedness

Category	Definition
Expected	An adverse event that is consistent with known information about the trial related procedures or rapid weight loss regimens.
Unexpected	An adverse event that is not consistent with known information about the trial related procedures or rapid weight loss regimens.

The CI or delegate will undertake review of all SAEs and may request further information from the assessing Trial Doctor for any given event to assist in this. If the event is unexpected (i.e., it is not defined in the protocol as an expected event) it will be classified as a related and unexpected SAE.

12.5.3. Provision of SAE follow up information

Following reporting of an SAE for a participant, the participant should be followed up until resolution or stabilisation of the event. Follow up information should be provided using the SAE reference number provided by the Trial Office.

12.6. Reporting SAEs to third parties

The independent Data Monitoring Committee (DMC) may review any SAEs at their meetings.

The Trial Office will report all events categorised as Unexpected and Related SAEs to the REC and Sponsor within 15 days of being notified.

12.7. Urgent Safety Measures

If any urgent safety measures are taken, the Trial Office shall immediately, and in any event no later than 3 days from the date the measures are taken, give written notice to the REC of the measures taken and the reason why they have been taken.

13. Data Handling and Record Keeping

13.1. Source data

Source data is defined as all information in original records and certified copies of original records of clinical findings, observations, or other activities in a clinical trial necessary for the reconstruction and evaluation of the trial. To allow for the accurate reconstruction of the trial and clinical management of participants, source data will be accessible and maintained.

In IIH-Advance, all trial data is being collected on the electronic CRFs on the EDC, therefore the electronic CRFs will be considered as source data. The exception will be for the OCT scans, where the source data will be the output report provided by and retained by Specsavers UK, and the original clinical letter stating the participant has IIH, which will remain with the participant.

Table 6: Source data in IIH-Advance

Data	Source
Participant Reported Outcomes	Obtained by participant direct entry, or interview directly with the participant for entry onto the EDC. The electronic CRF is the source data.
Height, weight	Obtained by interview directly with the participant for entry onto the EDC. The electronic CRF is the source data.
OCT Scans	The source is the original scan saved as an electronic file and stored by Specsavers UK in line with their usual processes. A report of this scan will be sent to the IIH-Advance trial team where it will be stored securely on University of Birmingham (UoB) research servers.
Clinical event data	Obtained by interview directly with the participant or by remote inspection of the participant's clinical letters for entry onto the EDC. The electronic CRF is the source data.
Recruitment	The original record of the randomisation on the electronic CRF is the source.

Change of Status	The change of status form on the electronic CRF is the source data. This form will be completed by Trial Researchers directly onto the EDC.
------------------	---

